1.0 PROTOCOL SUMMARY AND/OR SCHEMA

The goal of this study is to extend findings of propofol's effects on memory, as measured in volunteer research studies, to a clinical setting. Standard memory tasks utilized in clinical drug studies do not readily differentiate between effects on memory from sleepiness alone (sedation) or from a specific effect of certain drugs (e.g. benzodiazepines, propofol) on memory itself (amnesia). We have been able to differentiate these effects in adult volunteers using a visual picture task where intravenous infusion produced increasing drug concentrations over a period of approximately 10 minutes. We wish to assess the feasibility of using this behavioral paradigm in a clinical setting.

Very little research on the immediate memory effects of anesthetic drugs in pediatric patients has been done, as many tasks that test memory function are not suitable for pediatric patients, particularly in a busy clinical setting. The visual picture task used in our volunteer studies, on the other hand, is simple in nature and should be able to be performed easily by younger patients with minor disruption in procedure traffic.

We wish to assess the feasibility of a similar picture naming task in pediatric patients who require sedation for minor therapeutic procedures, principally MRI scans of the brain. Pediatric patients who are old enough to be able to name pictures will be offered inclusion in the study. Before the therapeutic procedure is begun, during induction of sedation, pictures will be shown to the child while they name them. This procedure will form memories as propofol concentration is increasing. After awakening following completion of the therapeutic procedure, recognition memory will be tested for the pictures presented as propofol sedation was being induced.

A control group of children of similar age and undergoing similar minor therapeutic procedures will be recruited to perform memory tasks as for the children who receive propofol.

2.0 OBJECTIVES AND SCIENTIFIC AIMS

1. The primary objective is to determine the feasibility of using the visual picture naming task in pediatric patients in the clinical setting. Feasibility will be defined as being able to accrue an average of 2 patients a week who successfully name and recognize sufficient numbers of pictures so that the thresholds for sedation and memory can be determined in each individual (as described in Section 11.0, Aim 1).
2. The strength of propofol amnesia (the effect of propofol on memory not related to sedation) will be estimated as a difference between thresholds for amnesia (loss of memory) and sedation (loss of verbal responsiveness)

MEMORIAL SLOAN-KETTERING CANCER CENTER IRB PROTOCOL

IRB#: 12-006A(5)

Hypothesis 1: The threshold effect for memory will occur significantly sooner, i.e. at lower drug concentrations, than the threshold effect for sedation, as illustrated in Fig 2 (the threshold for memory effect is illustrated by the light gray curves in the Figures, and for sedation by the dark curves).

3.0 BACKGROUND AND RATIONALE

Amnesia versus Sedation

One of the critical components of anesthesia is amnesia (lack of recall) for events during surgery or therapeutic procedures. The failure of this anesthetic effect, i.e. conscious awareness and recall of events during anesthesia, known as 'awareness', occurs at a low, but predictable frequency of ~0.5% both in adults and children. (1) In fact, the incidence of this complication may be higher in the pediatric population. (2) (3) Serious psychological sequelae may occur after an episode of awareness, with symptoms similar to those of post-traumatic stress disorder. (4) (5) (6) This eventuality may be particularly distressing for patients with cancer, who frequently require repeated therapeutic procedures. The fact that the incidence of awareness is so low makes it difficult to conduct systematic studies to address this issue. Thus, practice aimed at prevention of this complication is frequently based on expert opinion. One common recommendation is to use drugs with specific amnesic properties during anesthesia.

A more precise definition of an amnesic drug is one that is able to prevent recollection of memories at low or minimal levels of sedation. Amnesic drugs are useful adjuncts to other anesthetic agents, most of which prevent recall of intra-operative events on the basis of sedation alone, i.e. no conscious memories are formed because the patient is unable to experience and process stimuli from the outside world. However, periods of inadequate anesthetic level may occur for any number of reasons e.g. individual response to medications, sudden painful stimulus, hemodynamic instability necessitating decreased drug doses, refilling the drug delivery device, 'stormy' induction or emergence, etc. The rationale for the routine use of an amnesic drug is that it will prevent recall of any events occurring during periods of inadvertently light anesthesia. Midazolam is such an amnesic drug, and is frequently used in the therapeutic setting for this reason. Relative disadvantages of midazolam include relatively prolonged duration of action, of particular concern in the outpatient setting, and the inability to act as a suitable anesthetic agent when given alone. Propofol has been shown in many studies in adults to possess specific amnesic properties, both in the research and clinical settings. (7) (8) (9) (10) To date, propofol provides the most desirable qualities for an 'all-purpose' anesthetic agent, as it possesses amnesic properties, has a short duration of action, and can be administered as the sole anesthetic agent.

Sedation for therapeutic procedures in children

As propofol has desirable pharmacokinetic properties that allow deep levels of sedation commensurate with rapid recovery, it is the most common sedative agent given to pediatric patients for therapeutic procedures. However, almost no research has been done to determine if propofol is indeed an amnesic, as opposed to a purely sedative drug when

MEMORIAL SLOAN-KETTERING CANCER CENTER IRB PROTOCOL

IRB#: 12-006A(5)

given to pediatric patients. (11) There is evidence that the pharmacodynamics for propofol are different in children than adults, so the amnesic effects present in adults need to be confirmed in children. (12) Recently dexmedetomidine, an agent with a similarly favorable pharmacologic profile to that of propofol, has been introduced for sedation in pediatric patients. (13,14) Similarly to propofol, there is no research in pediatric patients regarding the memory effects of dexmedetomidine. In adult patients, the amnesic effect of dexmedetomidine is unclear, but there are some data to indicate that dexmedetomidine has few amnesic properties. (15) (16) (17) Interestingly, when dexmedetomidine was used for sedation in pediatric patients, improvement in the quality of sedation was noted when a known amnesic agent (e.g. midazolam or ketamine) was co-administered. (18,19) Whether this improvement may have been a result of the additional amnesic effect of these drugs, or some other property is unknown.

Thus, the possibility exists that using agents with amnesic properties may provide better quality of sedation in pediatric patients. The only way this hypothesis can be critically assessed is to have some measure of the amnesic effect of a given drug when given to pediatric patients in a clinical setting.

Measures of amnesic versus sedative effects

Sedative effects of anesthetic drugs can be measured in real time, for example by assessing reaction time, or presence of an adequate behavioral response while the drug is being given (e.g. keeping eyes open, or performing a simple task such as naming a picture). However, the assessment of memory is by definition retrospective. The memory effect of amnesic drugs develops over 10-30 minutes, and the full extent of memory impairment is only evident after this time interval has elapsed. (7,16) Measures of memory impairment due to a drug use recognition performance at some distinct time after the sedative effect of a drug was measured during administration. Thus, comparison of the amnesic and sedative properties of a drug represent behavioral responses obtained at two distinct time points. Modulation of the memory effect of a drug is related back in time to conditions present when the memory was being formed, i.e. at encoding. For the purposes of this study we are assessing modulation of memory by the degree of sedation present at encoding. (20) (21)

The methods used to assess the amnesic properties of drugs in the clinical setting are quite limited in comparison to controlled research settings. (22) Frequently measures of memory are used which cannot differentiate among the various factors that impair memory in the clinical setting. For example, anxiety in the peri-operative setting can itself impair memory for events before the administration of anesthesia. (23) Other difficulties in translation of methods to the clinical setting include the use of other drugs, timing of measurements, the presence of painful treatments, etc. (24) One of most difficult issues to address is the ability to separate the amnesic and sedative effects of drugs on memory. (25) (21) A behavioral paradigm that could separate sedative and amnesic effects of drugs easily applied in the clinical setting would allow the ability to measure the influence of the amnesic properties of a given drug on outcome, for example patient satisfaction with anesthesia or recall of procedure events. Over the past decade we have developed

MEMORIAL SLOAN-KETTERING CANCER CENTER IRB PROTOCOL

IRB#: 12-006A(5)

methods to measure amnesic versus sedative effects, in particular with propofol, in the research setting using volunteers. (7,16,21)

The drug ramping paradigm

A simple paradigm that allows amnesia to be differentiated from sedation is to infuse drug in increasing concentrations over a period of ~10 minutes. During this time period, as drug concentration and sedation are increasing, visual stimuli are presented. Importantly, these stimuli are attended to by performance of a task, in this case by naming a picture. A positive response on the task, naming the picture either correctly or incorrectly, confirms that the stimulus was processed sufficiently to be learned and allow testing for subsequent recognition.

The full range of sedation effects is achieved by administering the drug at a rate so that no sedation is present initially, with levels of sedation present that allow the naming task to be performed during the bulk of the infusion period. By the end of the infusion period sedation appropriate for the therapeutic procedure is present, namely, unresponsiveness to voice. Analysis of subsequent recognition memory and sedation at the time of encoding allows one to determine the time of picture presentation at which 50% memory effect occurs and compare it to the time at which 50% sedation occurs. The larger the separation between these two dose-response points, the greater are the amnesic properties present for the drug. This is illustrated below using exemplars from volunteer studies we have previously conducted.

[figure not shown]

FIG 1 Infusion of a typical **sedative** drug (**thiopental**) over 10 minutes, during which time 60 pictures were shown. As time increased (higher picture number), sedation increased, and fewer responses occurred (dark dots). Response data (response to picture task during infusion (yes/no) and subsequent recognition of picture, gray crosses) were fitted to regression curves. For sedative drugs, the subsequent lack of recognition memory parallels the increase in sedation, i.e. there was no specific amnesic effect (**a small difference in 50% effect** (horizontal black line) for memory and sedation)

[figure not shown]

FIG 2 Infusion of propofol (a typical **amnesic** drug) over 10 minutes, during which time 60 pictures were shown. As time increased (higher picture number), sedation increased only at the end of infusion (dark line). The hallmark of amnesia is the lack of subsequent recognition which begins well before any increase in sedation (dark line, **a large difference in 50% effect for memory and sedation**).

As there is substantial evidence that propofol is amnesic in adults and propofol is the most common sedative agent used for pediatric procedures, we wish to initially test the drug ramping paradigm as a measure of amnesic effect using propofol in pediatric patients. The main goal of this study is to determine the feasibility of patient accrual and ability to define the relationship of amnesia to the level of sedation.

In summary, a rationale exists, but is not proven, for the desirability of specific amnesic properties for drugs used during sedation/anesthesia. The development of an instrument to detect the amnesic effect of a given drug in a clinical setting would not only confirm results from previous volunteer studies, but would provide an opportunity to measure an important variable in patient outcome in terms of recall of the surgical/therapeutic experience, or of patient satisfaction. If the quality of amnesia does indeed relate to outcome, then this measure applied in the clinical setting would provide a rational basis for drug selection. Future studies could be used to compare drugs with similar pharmacokinetic profiles, for example, propofol with dexmedetomidine or various inhalational agents.

A protocol using the same methodology as in the current one is now open at Boston Children's Hospital, where dexmedetomidine is used for pediatric sedation. Accrual demographics are nearly identical with the patients accrued so far to the MSKCC protocol. Inclusion of a control group at both sites will validate a more direct comparison of memory effects from propofol with those of dexmedetomidine.

MEMORIAL SLOAN-KETTERING CANCER CENTER IRB PROTOCOL

IRB#: 12-006A(5)

Post-Operative Cognitive Dysfunction

Another important clinical issue is the presence of cognitive dysfunction after anesthesia in the elderly with impaired cognitive reserve. (26-28) (29,30) Memory impairment is an important component of post-operative cognitive dysfunction, which in turn is associated with a higher incidence of post-operative delirium, and poorer outcomes. (31) Of importance, patients of all ages who have received chemotherapy demonstrate varying degrees of cognitive impairment. (32) Thus, in theory, this patient population may be at similar risk to elderly patients with diminished cognitive reserve in terms of post-operative cognitive dysfunction. In fact, age, cognitive reserve and chemotherapy are all important determinants of cognitive performance. (33) If feasibility is demonstrated in the current protocol, the proposed behavioral paradigm could then be tested in a more heterogeneous adult patient population. The drug ramping paradigm could be a useful tool to assess the sensitivity of different patient populations to acute memory impairment by drug administration. The paradigm could be easily modified to assess memory function at various time points before and after intervention (as we have done to define memory decay characteristics in volunteers after receiving sedative and amnesic agents (16)). Substantial improvement in patient outcome may be possible if anesthetic management could be modified to decrease the incidence of POCD or delirium. Development of a behavioral measure of amnesia / memory dysfunction that can be easily applied in the clinical setting is a key component of this process.

4.0 OVERVIEW OF STUDY DESIGN/INTERVENTION

4.1 Design

Children either requiring sedation or not for therapeutic or diagnostic procedures will be offered inclusion in the study. Sedation will be induced over a period of 10 minutes by administering propofol at an infusion rate that will produce suitable conditions for the procedure at the end of infusion (heavily sedated or asleep). During the infusion pictures will be shown to the child who will be encouraged to name the item in the picture. After completion of the procedure, when the child is awake and being assessed for discharge, memory will be tested using forced choice recognition of pictures previously shown intermixed with novel pictures. The child will indicate yes/no whether the picture was seen during induction of sedation. Children not requiring sedation will perform exactly the same tasks as described above, but without any drug infusion.

4.2 Intervention

During induction of sedation, or in the case of no sedation, before the therapeutic procedure, children will be encouraged to name the items shown in pictures displayed, one every 5 seconds, as drug concentration is increasing. Naming pictures will ensure that items are being attended to and memory systems are engaged. The child's response will be used to assess the degree of sedation present (response present / response absent). After recovery from sedation, or after a similar time period after the therapeutic procedure

MEMORIAL SLOAN-KETTERING CANCER CENTER IRB PROTOCOL

IRB#: 12-006A(5)

(approximately 40 min) for children in the control group memory for the previously presented pictures will be tested using a yes/no response. The recognition testing set will contain both previously seen and novel items.

5.0 CRITERIA FOR SUBJECT ELIGIBILITY

Describe the characteristics of the subject population.

5.1 Subject Inclusion Criteria

- The patient must be between 4 and 14 yrs of age and be undergoing a therapeutic or diagnostic procedure with or without sedation
- The patient must be able to comprehend and perform the task (naming pictures)
- The patient must have a minimum weight of 8 kg

5.2 Subject Exclusion Criteria

- Allergy to propofol (for those patients requiring sedation)
- Procedure of short duration (< 15 min)
- Pregnancy
- Recent use (within 5 half-lives) of centrally acting medications that could affect concentration (e.g. diphenhydramine)

6.0 RECRUITMENT PLAN

Pediatric patients undergoing therapeutic or diagnostic procedures that might require sedation will be offered inclusion in the study on the day of the procedure upon arrival to the Pediatric Day Hospital. It is anticipated that between 2 and up to 5 patients a week will participate in this study.

7.0 ASSESSMENT/EVALUATION PLAN

The recognition memory task will consist of simple line drawings selected from a larger stimulus data base (<http://crl.ucsd.edu/experiments/ipnp/method/getpics/getpics.html>) based on their age appropriateness and identifiability by children in the target age range. Stimulus items are presented by means of a bound stimulus book with one black and white line drawing presented on each page. A brief test will be performed to familiarize the child with performing the picture naming task, using different pictures from those that will be shown in the study. If the child is not able to cooperate sufficiently with the test task, then he/she will be withdrawn from the study and propofol will then be administered as per normal clinical practice for their procedure. If sedation will be needed, propofol infusion will be started at a rate to deliver 3mg/kg over a 10 minute period. During this learning phase of the study, pictures will be presented to the participant and the participant will be asked to name each object pictured with accuracy and non responses will be recorded by the examiner. If sedation is being given, the drug infusion rate will be adjusted according to clinical observation (e.g. excessive sedation/no drug effect apparent) so that the patient will be appropriately sedated for the planned procedure by the end of the 10 minute infusion period. After conclusion of the initial infusion, propofol will be administered as per usual practice. Following the procedure after awakening in the PACU, when no apparent sedation is

Amended: 6/10/13

MEMORIAL SLOAN-KETTERING CANCER CENTER IRB PROTOCOL

IRB#: 12-006A(5)

present, or after a similar time period, if no sedation was used, the picture recognition phase of the study will be performed. Patients will again be presented the original pictures with an equal number of pictures not seen during the infusion phase. The order of pictures in the learning (propofol infusion) and recognition phases(PACU) will be the same for every patient. The child will indicate whether the picture was seen before (yes/no). The study is complete. The child will be discharged form the PACU as per standard clinical criteria."

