where $\alpha > 0$ and $\beta > 0$ are the scale and shape parameters, respectively, and $x \geq 0$. (35) The constant of 0.5 assumes a 50-50 chance of a random response in a psychophysical task. Conventionally, the median of $F(x)$ is called the “threshold” of the underlying psychometric function (the value of x for which $F(x) = 0.5$). Because of the assumed 0.50 constant in $G(x)$, and the 0.5 times the median of the Weibull, the threshold estimate is the x value of an overall 75% response probability given the Weibull parameters. The threshold of a psychometric function generally represents the strength of stimulus that elicits a sensation or a noticeable difference. In this case the sedation threshold represents the time value of x when sedation is actuated. We will estimate one sedation curve and its corresponding threshold for each child.

MEMORIAL SLOAN-KETTERING CANCER CENTER IRB PROTOCOL

IRB#: 12-006A(5)

2. "Memory threshold": When the anesthesia has worn off at approximately 1 hour later, the child will be presented with another list of 120 pictures with half having been presented during the initial infusion of propofol. At the presentation of each picture, the child will be asked whether or not he/she remembers having seen it previously. Each response will be coded as correct (true positives and true negatives) or incorrect (false positives and false negatives). A curve may be fitted to the memory recognition data to estimate the average memory decay function for each child. In Figure 1 and 2 this is represented as the light gray curve, which can be modeled as $1 - G(x)$ above. Similarly, a threshold represents the time value (picture number) when memory fades below threshold.

The *sedation* threshold in Figure 1 is at image 25 (250 seconds), while the *memory* threshold is at approximately image 28 (280 seconds). This 30-second / 3 picture difference is taken to represent that sedation occurs concurrently with memory decay. Alternatively, in Figure 2, the *sedation* threshold is at image 58 (580 seconds) while the *memory* threshold is approximately at image 40 (400 seconds). This larger difference of 180 seconds / 18 pictures is a measure of how much sooner amnesia occurred in this instance than sedation. In this latter case, a measurable amnesic effect of 180 seconds can be inferred from the two threshold values.

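### The propofol rate is adjusted to observed sedation during the picture task, so the size of the threshold gap in seconds partly reflects the adjustment; log rate changes and report the gap in mg/kg beside it

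*Combined protocol and SAP*

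**What the plan says.** Section 7.0 fixes only the start of the infusion: "propofol infusion will be started at a rate to deliver 3mg/kg over a 10 minute period". While the pictures are being shown, "the drug infusion rate will be adjusted according to clinical observation", either because the child is too sedated or because no effect is visible, "so that the patient will be appropriately sedated for the planned procedure by the end of the 10 minute infusion period". The size, timing and number of changes are left open.

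The analysis is on a time scale. For the sedation curve, section 11.0 (Aim 2) states: "In this case the sedation threshold represents the time value of x when sedation is actuated". Of the Figure 2 example it says: "This larger difference of 180 seconds / 18 pictures is a measure of how much sooner amnesia occurred in this instance than sedation".

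The hypothesis in section 2.0, repeated in section 11.0, treats time and concentration as interchangeable: "The threshold effect for memory will occur significantly sooner, i.e. at lower drug concentrations, than the threshold effect for sedation".

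The size of the gap carries meaning in three places. Section 2.0 defines the strength of amnesia as the threshold difference, and section 3.0 reads a wider separation as a stronger amnesic property. Section 9.0 names the variability of the two thresholds across children as an important goal. Section 3.0 also looks ahead to a comparison with dexmedetomidine at a second site.

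No section provides for recording rate changes for analysis, converting time to dose or modelled concentration, adjusting for rate, or examining children with an unchanged rate separately. Section 14.0 refers to targeted concentrations but gives no target and no pharmacokinetic model.

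**The concern.** Elapsed time maps to exposure in the same way for every child only if every child gets the same weight-based rate throughout. Here the rate responds to sedation, which is one of the two measured outcomes, and it is steered so that sedation arrives near a fixed time. Two children with identical sensitivity can therefore have different gaps in seconds because the infusion was handled differently.

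What is at stake is the interpretation of the effect size: the mean gap as a measure of amnesic strength, its spread between children, and any comparison with another drug given under a different infusion practice. Rate changes that are not recorded at the time may not be recoverable later.

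**Working it through.** **The plan's own figure.** Section 11.0 states 80% power for a one-sample t-test with n = 35, mean 0.50, SD 1.0 and two-sided alpha 0.05. The noncentrality is 0.50 × √35 = 2.96 on 34 degrees of freedom, and the exact power is 0.82. The figure reproduces.

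**Inputs for the illustration.**
- Starting rate (section 7.0): r = 3 mg/kg ÷ 600 s = 0.005 mg/kg/s.
- Figure 2 thresholds (section 11.0): memory 400 s, sedation 580 s.
- Assumption: effect follows cumulative dose, with no elimination.
- Assumption: the Figure 2 times are read as if obtained at r. Figure 2 comes from earlier volunteer work, and its infusion rate is not given.
- Assumption: rate multiplier m and change time tc.

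**Dose thresholds.** Memory: 400 × 0.005 = 2.0 mg/kg. Sedation: 580 × 0.005 = 2.9 mg/kg. The gap is 0.9 mg/kg.

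**Time to reach dose D.** t = D/r if D is reached before tc; otherwise t = tc + (D − r·tc)/(m·r). If the change comes at or before the memory threshold, the time gap is 0.9/(m·r), whatever tc is.

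| Rate path | Memory | Sedation | Gap |
|---|---|---|---|
| constant | 400 s | 580 s | 180 s |
| ×1.25 from 300 s | 380 s | 524 s | 144 s |
| ×1.5 from 200 s | 333 s | 453 s | 120 s |
| ×1.5 from 300 s | 367 s | 487 s | 120 s |
| ×1.5 from 400 s | 400 s | 520 s | 120 s |
| ×1.5 from 450 s | 400 s | 537 s | 137 s |

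In every row the gap in dose is 0.9 mg/kg.

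**What survives.** Under this model, with any positive rate, a zero dose gap is a zero time gap, and a positive dose gap is a positive time gap. The null and the sign are preserved.

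**Effect on the t-test.** Take the planning values and multiply each child's gap by a factor independent of that gap (an assumption). With 2/3, 1 and 4/3 in equal thirds, simulated power is 0.79. With 2/3 and 4/3 in halves it is 0.78. With 2/3 for everyone it is 0.82, because a common factor scales mean and SD alike. Type I error stays at about 0.05.

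**Dependence on the model.** With first-order loss of 0.1 per minute (assumed), ×1.5 from 300 s gives a gap of about 85 s rather than 120 s. With loss of 0.3 per minute (assumed) and ×0.8 from 300 s, concentration levels off and neither threshold is reached. The size of the distortion, and the protection of the ordering, depend on kinetics that the documents do not supply.

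**The time scale itself.** Section 4.2 and the sedation part of Aim 2 show one picture every 5 s. The worked example in section 11.0 puts image 58 at 580 s, which is 10 s per picture. The recognition list of 120 is half previously shown, so 60 pictures last 60 × 5 = 300 s or 60 × 10 = 600 s. At the starting rate, picture 58 corresponds to 58 × 5 × 0.005 = 1.45 mg/kg or 58 × 10 × 0.005 = 2.9 mg/kg.

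**The case against.** The strongest reply is that Hypothesis 1 is an ordering within each child, tested against zero. That ordering holds while drug accumulates, and the simulated loss of power is small. This stands. A reader might infer that titration biases the test or badly erodes its power. An added independent SD of 0.75 would indeed lower power to 0.63, but nothing in the documents supports that value. Steering sedation toward 10 minutes could equally reduce the spread.

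A reader might also present the distortion as symmetric, 33% either way, by adding a rate cut to 0.75 times, which gives 240 s. That does not hold for the Figure 2 child. Someone who loses response at 580 s is not over-sedated at 200 to 400 s, and the cut moves sedation to 640 to 707 s, which misses the aim stated in section 7.0.

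A third tempting step is to make cumulative dose the primary scale. Controls receive no drug, so all their pictures would sit at dose zero and no curve could be fitted, yet Aim 1 requires usable curve parameters from controls too. Cumulative dose also cannot fall when a rate cut lets concentration fall.

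Finally, the primary objective is feasibility, section 9.0 calls it premature to expect a reliable threshold difference, and section 3.0 defines the ramp by behavioural endpoints. These points lower the priority. They do not make a gap in seconds comparable between children whose rates were changed differently.

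**Conclusion.** The point holds for the size of the gap and hardly touches the hypothesis test. As written, Aim 2's strength of amnesia, its between-child variability and any later comparison with dexmedetomidine mix drug sensitivity with how the rate was adjusted. In the illustration one fixed dose gap reads as 180 s or 120 s, a one-third reduction. This rests on three assumptions: effect following cumulative dose, a volunteer figure read at the paediatric starting rate, and a chosen multiplier of 1.5. The actual size cannot be derived from the documents, because the frequency, timing and extent of rate changes are not specified. The protection of the ordering can fail if a rate cut lets concentration level off or fall. This is a cheap improvement to data capture and reporting. The planned t-test need not be replaced.

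**What to change.** - Record the clock time and new value of every rate change during the 10-minute infusion. Section 8.0 says that an infusion pump is used but not that it stores this history, so the study must collect it.
- For the propofol group, derive cumulative mg/kg at each picture. Prespecify the threshold difference in mg/kg as a supporting analysis beside the time-scale result.
- Summarise the time-scale result separately for children with and without rate changes.
- Keep time or picture number as the common scale, because control curves can be fitted only there.
- Reconcile the seconds-per-picture figures in sections 4.2 and 11.0 before computing either scale.

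Clinical dosing is unchanged. The cost is a few data fields and one derived variable. Cumulative dose remains only a proxy for concentration, and it is weakest after a rate cut.
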